24-hr urine collection ^e	X											X	X ^f	One collection is needed as soon as possible during Screening. Two collections must be obtained within 2 weeks prior to Week 26 (Section 8.2.1)
Morning spot urine sample ^e	X	X	X	X	X	X	X	X	X ^g	X	X	X		Obtain sample prior to dosing, vaccination, and biopsy
eGFR	X	X	X	X	X	X	X	X	X	X	X	X ^f		One additional blood draw for eGFR (serum creatinine) is required within 2 weeks prior to the Week 26 visit.
Monitor for Renal and Extrarenal SLE Flare ^f		Continuous monitoring										X		Refer to Section 3.2.1 and 3.2.2 for definitions. Document use of additional standard of care therapy and/or repeat biopsy ^f , if applicable.
Blood sample for C3, C4, and CH50	X	X		X			X		X		X	X		
Safety Assessments														
Physical examination	X	X										X		
Abbreviated PE			X	X	X	X	X	X	X	X	X			
Vital signs ^h	X	X	X	X	X	X	X	X	X	X	X			

Table 1: Schedule of Activities During the Initial Evaluation Period: Screening to Week 26 Visit (LN Cohort)

Period	Screening	Initial Evaluation Period											Eval. for Renal Flare and Extrarenal SLE Flare	Notes
Visit	1	2	3	4	5	6	7	8	9	10	11			
Week	Up to 6 W		W1 ^a	W2	W4	W6 ^b	W10	W14	W18	W22	W26/ED ^c			
Days and Window	D -42 to -1	D1	D8 ± 2	D15 ± 3	D29 ± 3	D43 ± 5	D71 ± 5	D99 ± 5	D127 ± 5	D155 ± 5	D183 ± 5			
ECG ⁱ	X											X		
Prior medications and procedures	X													
Concomitant medications, nonpharmacologic therapies, and procedures		Continuous monitoring											X	
Adverse events	Continuous monitoring											X		
Clinical chemistry	X	X	X	X	X	X	X	X	X	X	X	X		
Hematology and coagulation	X	X	X	X	X	X	X	X	X	X	X			
Urinalysis and sediment	X	X	X	X	X	X	X	X	X	X	X	X	Obtain sample from a morning void prior to dosing	
Participant safety card review		X	X	X	X	X	X	X	X	X	X	X	Confirm participants carry safety card at all times	
Pharmacokinetic and Pharmacodynamic Assessments														
Blood samples for PK/PD ^j		B/P	X	T/P	X		T/P		T/P		T	X	Samples can be obtained anytime at ED Visit	
Blood samples for ADA		B			X		T				T		Samples can be obtained anytime at ED Visit	
Exploratory Assessments														
EQ-5D-5L		X					X				X			
SF-36		X					X				X			
FACIT-Fatigue		X									X			

Table 1: Schedule of Activities During the Initial Evaluation Period: Screening to Week 26 Visit (LN Cohort)

Period	Screening	Initial Evaluation Period										Eval. for Renal Flare and Extrarenal SLE Flare	Notes	
Visit	1	2	3	4	5	6	7	8	9	10	11			
Week	Up to 6 W		W1 ^a	W2	W4	W6 ^b	W10	W14	W18	W22	W26/ED ^c			

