6.5.1. Allowed Concomitant Therapy for LN Cohort

During the course of the study, participants in the LN cohort will receive allowed concomitant therapy consistent with the standard of care for induction and maintenance treatment of LN.

- For participants who have not started corticosteroid induction treatment prior to Screening:
 - Participants will receive a cumulative dose of 1 gram of methylprednisolone IV administered in 1 or multiple divided doses or oral equivalent during the Screening Period (prior to Day 1).
 - During the Screening Period and no later than Day 2, all participants will receive oral corticosteroids with prednisone or prednisone equivalent with starting doses as outlined in **Table 10**. The starting minimum and maximum dose allowed are 30 mg/day and 60 mg/day, respectively. A corticosteroid taper will commence on Week 2 (Day 14). From Week 12 to Week 26, the target dose is 7.5mg/day. Following Week 26, participants may remain on 7.5 mg/day or continue to taper at the clinical discretion of the Investigator until Week 46. From Week 46 to Week 50, the dose of corticosteroids must not be changed.
 - During the Screening Period and no later than Day 1, participants will receive a cumulative dose of 1 to 1.5 g/day of MMF any time after completion of the IV

methylprednisolone during the Screening Period and no later than Day 1. The dose can be administered in multiple divided doses. Participants will continue to receive 1 to 1.5 g/day for 1 week.

- After receiving 1 to 1.5 g/day for 1 week, the dose will be increased per the discretion of the Investigator to a cumulative dose of 2 to 3 g/day of MMF no later than by Week 4 (Day 28). The dose can be administered in multiple divided doses. Participants will continue to receive 2 to 3 g/day of MMF until Week 50 after which it may be decreased or discontinued based on the Investigators' judgment and the Kidney Disease Improving Global Outcomes (KDIGO) clinical practice guidelines ([KDIGO, 2021](#)).
- For participants who have initiated corticosteroid induction treatment prior to Screening and do not meet Exclusion Criterion 20 (Section [5.2.2](#)):

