8.2. Efficacy Assessments

8.2.1. 24-hour Urine Collection

For the determination of proteinuria, 24-hour urine collection will be obtained during Screening, Week 26, and Week 50, and will be analyzed by a central laboratory. In addition to protein, albumin, sodium, and creatinine will also be quantified in each of the 24-hour urine collections. Both UPCR as well as albumin to creatinine ratios (UACRs) will also be calculated in an aliquot of the 24-hour urine collection.

Rigorous exercise and significant change in diet (in particular, salt intake) should be avoided within 48 hours before collection of 24-hour urine samples, whenever possible.

The collection should be obtained prior to or > 7 days after biopsy procedures and prior to administration of ravulizumab or placebo on dosing days.

The 24-hour urine collections could occur at the participant's home by a mobile nurse if agreed upon with the Investigator and the participant, according to local regulations. The collection will be recorded in the CRF according to the CRF completion guidelines.

LN Cohort

For participants in the LN cohort, proteinuria will be measured by UPCR. A single 24-hour urine collection will be obtained at Screening to assess eligibility. Two separate 24-hour urine collections will be obtained within 2 weeks prior to the Week 26 Visit (to assess the primary endpoint) and Week 50 Visit (to assess a secondary endpoint).

Confirmation of a protocol-defined Renal Flare or Suboptimal Response requires a single 24-hour urine collection within 2 weeks of the spot urine sample (Section 3.2.1 and Section 3.2.3).

IgAN Cohort

Participants in the IgAN cohort will be required to provide 2 separate complete and valid 24-hour urine collections during the Screening Period (to assess eligibility), at Week 26 (to assess the primary endpoint), and at Week 50 (to assess a secondary endpoint). The 2 valid 24-hour urine collections should be obtained within 2 weeks before the Week 26 and Week 50 Visits.

Completeness of the 24-hour urine collection will be estimated from rate of creatinine excretion. Normal values of creatinine excretion vary with age and body weight. Hence, a 24-hour urine collection is considered valid if all the following criteria are met, otherwise the urine collection is required to be repeated:

- The collection is between 22 to 26 hours in duration (ie, time from the initial discarded void to the last void/attempt to void).

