2. STATISTICAL HYPOTHESES

The primary hypothesis for this study is that ravulizumab is superior to placebo in decreasing proteinuria. Hypothesis testing will be one-sided and performed at the 0.05 level of significance.

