3. SAMPLE SIZE DETERMINATION

This study plans to enroll 60 participants in both the IgAN and LN cohorts in a 2:1 ratio to ravulizumab and placebo for a total of 120 participants.

In March 2018, a National Kidney Foundation-sponsored workshop on surrogate endpoints for clinical studies in early stages of chronic kidney disease proposed that a 20% to 30% reduction in the geometric mean of albuminuria or proteinuria was likely to be necessary to ensure a significant treatment effect on the clinical outcome ([Levey, 2020](#)).

Individual patient data from relevant studies in IgAN was previously used to estimate variability and expected changes in proteinuria for patients treated with placebo in addition to background standard-of-care treatment ([Fellstrom, 2017](#)). Based on these data, the geometric mean (GM) of the ratio of 26-week to baseline proteinuria values is assumed to be 0.85 (ie, a 15% reduction in proteinuria) for the placebo treatment group. In order to target at least a 30% relative treatment effect (ie, 1 minus geometric mean ratio [GMR] of ravulizumab to placebo at Week 26), the GM of the ratio of 26-week to baseline is assumed to be 0.55 (ie, a 45% reduction in proteinuria) for the ravulizumab treatment group.

Expected changes in proteinuria and associated variability were not available on the log-scale for patients with LN; however, 2 studies of patients with LN who were treated with mycophenolate mofetil (MMF) showed mean proteinuria values of approximately 4.0 g/day at baseline and approximately 2.0 g/day at Week 24 ([Appel, 2009](#); [Ginzler, 2005](#)). The GM of the ratio of 26-week to baseline proteinuria values is assumed to be 0.60 (ie, a 40% reduction in proteinuria) for the placebo treatment group. In order to target at least a 30% relative treatment effect, the GM of the ratio of 26-week to baseline proteinuria values is assumed to be 0.40 (ie, a 60% reduction in proteinuria) for the ravulizumab treatment group.

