Sample size calculations are based on a 1-sided, 2-sample t-test of log-transformed proteinuria values. The log change from baseline in proteinuria is calculated as $\log(0.85)$ and $\log(0.55)$ for the placebo and ravulizumab treatment groups, respectively, for the IgAN cohort and as $\log(0.60)$ and $\log(0.40)$ for the placebo and ravulizumab treatment groups, respectively, for the LN cohort. A common standard deviation (SD) of log change is assumed to be 0.60 ([Fellstrom, 2017](#)). Under these assumptions and an anticipated 10% drop out rate, a sample size of 60 participants (40 participants randomized to ravulizumab, 20 participants randomized to placebo) will provide approximately 80% power to detect a treatment difference with a 1-sided significance level of 0.05 in each cohort.

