5.3.2. Main Analytical Approach

The primary analysis of the primary efficacy endpoint (percentage change from baseline in proteinuria at Week 26) will be conducted for each disease-specific cohort after all participants have completed the protocol-required assessments in the Initial Evaluation Period.

For the primary efficacy endpoint, when two 24-hour urine collections are required and only 1 collection is available at the visit, then this value will be used for analysis. When more than 2 collections are available at the visit, only 2 valid collections recorded in the eCRF will be used for analysis.

To reduce skewness, the natural logarithm will be used to transform proteinuria values before analysis. An analysis of covariance (ANCOVA) will be used for the primary efficacy endpoint to compare reductions in proteinuria between the ravulizumab and placebo treatment groups. The ANCOVA model will include change from baseline in log-transformed proteinuria as the response variable and will adjust for baseline log proteinuria and the randomization stratification factor. The treatment effect will be evaluated using the least squares mean difference between treatment groups. The point estimate and 2-sided 90% confidence interval (CI) for the mean difference of log-transformed proteinuria will be back transformed (via exponentiation) to obtain the GMR and corresponding 2-sided 90% CI. The values will then be expressed as percentage change in adjusted geometric mean of proteinuria at Week 26 relative to baseline.

Data collected on or after receipt of additional standard-of-care therapy (for LN cohort) will be imputed using the proteinuria value from the 24-hour urine collection performed at the time of renal flare or extrarenal SLE flare. Data collected on or after treatment discontinuation will be assumed MAR and imputed using multiple imputation.

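### LN primary ANCOVA: the Day 1 pre-dose spot UPCR, already scheduled for everyone, is an unused baseline covariate that could add precision

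*SAP*

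**What the plan says.** **Model.** SAP 5.3.2 analyses change in log proteinuria at Week 26 by ANCOVA that "will adjust for baseline log proteinuria and the randomization stratification factor". The code in SAP 6.4.1 has treatment, baseline and stratum only. Protocol 9.4.1.1 specifies the same model. The multiple-imputation code in SAP 6.4.3 uses treatment, baseline, stratum and the Week 26 value. The models in 6.4.4 and 6.4.5 draw on the same baseline variables.

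**LN baseline.** Protocol 8.2.1: "A single 24-hour urine collection will be obtained at Screening to assess eligibility". SAP 5.3.1 uses that one value as LN baseline and the mean of two collections at Week 26. The IgAN cohort has two collections at both times. On timing, the LN schedule (Protocol Table 1) says: "One collection is needed as soon as possible during Screening". Screening lasts up to 6 weeks.

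**Treatment before Day 1.** Under Protocol 6.5.1, participants not yet on corticosteroid induction receive IV methylprednisolone (or oral equivalent) during Screening. MMF starts no later than Day 1 and oral corticosteroid no later than Day 2. The others arrive with induction under way. The LN stratification factor separates these two groups.

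**Spot urine.** Protocol Table 1 schedules a morning spot sample at Screening, on Day 1 before dosing, and at later visits. SAP 5.4.1 uses spot UPCR in a secondary repeated-measures model, and SAP 5.4.6, 5.5.5 and 5.5.7 use it for time-to-event endpoints.

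**The concern.** ANCOVA gains precision when its covariates predict the outcome. Here the one proteinuria covariate is a single measurement, possibly several weeks old at randomisation, with immunosuppression starting or continuing in between. The stratum term shifts the mean by induction timing, but it cannot record how far each participant's proteinuria has moved.

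The Day 1 sample is taken before study drug, so treatment cannot affect it and it is a legitimate covariate. It is a second reading of baseline proteinuria and also picks up any early response to induction. Leaving it out keeps that variation in the error term. With 20 placebo participants planned, and a Week 26 analysis meant to inform Phase 3 planning, the width of the interval matters.

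**Working it through.** **1. Inputs from the plan (SAP 2 and 3).** "Hypothesis testing will be one-sided and performed at the 0.05 level of significance". "Sample size calculations are based on a 1-sided, 2-sample t-test of log-transformed proteinuria values". The LN Week 26 to baseline ratio "is assumed to be 0.60 (ie, a 40% reduction in proteinuria) for the placebo treatment group" and "is assumed to be 0.40 (ie, a 60% reduction in proteinuria) for the ravulizumab treatment group". The SD of log change is 0.60, and 60 are randomised as 40 and 20. With 10% dropout, 36 and 18 remain.

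**2. The plan's own power figure.**
- Difference: ln(0.60/0.40) = 0.4055.
- Standard error: 0.60 × √(1/36 + 1/18) = 0.1732.
- Noncentrality: 0.4055/0.1732 = 2.341.
- With 52 df the one-sided critical value is 1.675, and the noncentral t gives **74.7%** (normal approximation 75.7%). The plan states approximately 80%.
- At 40 and 20 with no dropout: 78.6%.
- The same method for IgAN, ln(0.85/0.55) = 0.4353 at 36 and 18, gives 79.8%, which agrees with the plan.

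**3. Effect of an added covariate.** If log Day 1 spot UPCR explains a share R² of the variance left by the planned covariates, the residual SD becomes 0.60 × √(1 − R²). The documents do not give R², so the table shows a range. It takes 0.60 as the residual SD of the planned ANCOVA.

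| Partial R² (assumed) | Residual SD | Interval narrower by | Power at 36/18 | Equivalent evaluable N, 54/(1 − R²) |
|---|---|---|---|---|
| 0 | 0.600 | 0 | 74.7% | 54 |
| 1% | 0.597 | 0.5% | 75.1% | 54.5 |
| 5% | 0.585 | 2.5% | 76.6% | 56.8 |
| 10% | 0.569 | 5% | 78.5% | 60 |
| 15% | 0.553 | 8% | 80.5% | 63.5 |
| 20% | 0.537 | 11% | 82.6% | 67.5 |

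A partial correlation of about 0.37 (R² about 14%) is needed to reach 80%.

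**4. Cost if it is uninformative.** Charging a degree of freedom for each covariate, power goes from 74.67% (50 df) to 74.65% (49 df). A 20,000-run ANCOVA simulation, which also allows for chance imbalance in the covariates, gave 73.1% without the term and 72.3% with it, a loss of about 1 point.

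**5. How large could R² be?** All inputs in this step are assumptions.
- Let the Screening value be B + e₁, the Day 1 spot value B + I + e₂, and the Week 26 outcome carry k(B + I). B is the participant's true log level and I the early induction response.
- With v = var(B)·var(e₁)/(var(B) + var(e₁)), R² = k²(v + var(I))² / [(v + var(I) + var(e₂)) × 0.36].
- SDs tried: B 0.5 to 0.8, e₁ 0.2 to 0.3, I 0.2 to 0.4, e₂ 0.35 to 0.5.
- Highest case, k = 1: v = 0.64 × 0.09/0.73 = 0.079, so R² = 0.239²/(0.361 × 0.36) = 44%.
- Lowest case, k = 1: v = 0.25 × 0.04/0.29 = 0.0345, so R² = 0.0745²/(0.3245 × 0.36) = about 5%.
- With half carry-over to Week 26 (k = 0.5) the range is about 1% to 11%. With a quarter it is about 0.3% to 2.7%.

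**The case against.** The strongest reply is that this is a modelling preference. Adjusting for the endpoint's own baseline and the stratification factor is standard, prespecified and valid. That is correct, and no bias is claimed.

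Several more specific objections also stand:

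- **The stratum is in the model.** It already absorbs the mean difference between the two induction groups.
- **The Screening sample may not be pre-induction.** A reader might infer that it always is, and that Day 1 follows completed induction. The documents do not support this. Eligibility covers people already receiving induction (Protocol 5.1.2), the collection is not tied to the start of induction, and MMF and oral steroid may start as late as Day 1 and Day 2. LN participants are also randomised as soon as eligibility is confirmed, so Day 1 may reflect only a few days of treatment.
- **The gain may be small.** A spot sample is likely to be noisier than a 24-hour collection, and 26 weeks of background therapy may dilute what Day 1 predicts. With quarter carry-over the gain is about 1 point or less.
- **Spot UPCR is not ignored.** The secondary model in SAP 5.4.1 adjusts for baseline, and the general definition in SAP 6.1.2 makes that normally the Day 1 value.
- **Some Day 1 samples may be missing or unusable.** Spot urine must be taken before a biopsy or more than 7 days after it (Protocol 8.2.2), and the LN biopsy may fall in Screening.

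These points limit the size of the gain and shape the wording of the fix. They do not remove the case for using a baseline measurement already scheduled for everyone, at very low cost.

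**Conclusion.** The point holds as a worthwhile efficiency improvement. The LN primary model and its imputation models omit a pre-treatment proteinuria measurement taken closer to randomisation than the covariate they use.

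The gain ranges from negligible to several points of power: about 75% to 83% for an assumed partial R² of 1% to 20%, against 74.7% without the term. The downside is at most about 1 point. The values depend on the assumed R² and on treating 0.60 as the residual SD.

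That second assumption also limits a stronger reading, that LN is underpowered and needs this covariate. The stated 80% does not reproduce from the plan's t-test inputs after dropout. But 0.60 is an unadjusted SD, and SAP 3 says no log-scale LN variability was available. If the planned covariates already explain about 14% of the variance, the residual SD is 0.60 × √0.86 = about 0.557, and the planned ANCOVA reaches 80% at 36 and 18. The power shortfall is a separate sizing question and does not show that the planned analysis is deficient.

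**What to change.** Before any unblinded LN data are seen, including at the optional early LN interim analysis (SAP 5.8.3):

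1. Add log(Day 1 pre-dose spot UPCR) as a further continuous covariate in the LN primary ANCOVA (SAP 5.3.2 and 6.4.1), and align Protocol 9.4.1.1 or record the change in SAP 6.5.
2. Add the same variable to the LN imputation models in SAP 6.4.3 to 6.4.5, so that imputation and analysis models match.
3. State the rule for a missing or unusable Day 1 sample, including one taken within 7 days after a biopsy: use the last pre-dose spot value.
4. Keep the current model as a sensitivity analysis.

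The 24-hour endpoint and its Screening baseline do not change. The cost is one degree of freedom, one missing-data rule and a short amendment. For participants who need the fallback, the covariate is an earlier reading and likely to be less informative. If unblinded LN results have already been seen, report the extended model as supportive only.

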5.3.3. Sensitivity Analysis

[Table 2](#) shows the sensitivity analyses that will be produced for the primary endpoint.

Table 2: Sensitivity Analyses

Sensitivity Analysis	Methodology	Population	Handling of Intercurrent Events
Placebo-based multiple imputation	ANCOVA	FAS	
- Data collected on or after receipt of additional standard-of-care therapy (for the LN cohort only) will be imputed using the value collected at the time of renal flare or extrarenal SLE flare- Data collected on or after treatment discontinuation will be imputed using placebo-based multiple imputation
Tipping point analysis	ANCOVA	FAS	
- Participants who receive additional standard-of-care therapy (for the LN cohort only), discontinue treatment, withdraw early or die are assumed to have outcomes that are worse than otherwise similar participants who remain in the study or did not receive additional standard-of-care therapy or discontinue treatment

Table 2: Sensitivity Analyses

Sensitivity Analysis	Methodology	Population	Handling of Intercurrent Events
Per-randomized stratification analysis	ANCOVA	FAS	
 - Data collected on or after receipt of additional standard-of-care therapy (LN cohort only) will be imputed using the value collected at the time of renal flare or severe extrarenal SLE flare - Data collected on or after treatment discontinuation will be imputed using multiple imputation

Abbreviations: ANCOVA = analysis of covariance; FAS = Full Analysis Set; LN = lupus nephritis; SLE = systemic lupus erythematosus

Further details of these sensitivity analyses are below.

- Placebo-based multiple imputation: The primary endpoint will be analyzed in the same manner as the primary analysis, except data collected on or after treatment discontinuation will be assumed missing and imputed using placebo-based multiple imputation where it will be assumed that outcomes occurring after treatment discontinuation will follow the trajectory of outcomes similar to the one in the placebo treatment group, taking into account observed values prior to treatment discontinuation ([Ratitch, 2014](#)).
- Tipping point analysis: An additional sensitivity analysis will be performed based on the delta-adjusted stress testing method (tipping point analysis). This approach assumes that patients who discontinue from ravulizumab treatment or who receive additional standard-of-care therapy (for the LN cohort only) experience worsening, defined by a prespecified adjustment (delta) in the primary efficacy endpoint compared with the observed efficacy score of patients that continue the study to next visit. For each value of delta, the treatment effect will be determined, and the value of delta for which the nominal 2-sided p-value crosses 0.10, will be considered as the ‘tipping point’ in the sense that the conclusion drawn from the primary analysis is reversed when patients who drop out or who receive additional standard-of-care therapy are assumed to experience this fixed adjustment after the discontinuation visit or receipt of additional standard-of-care therapy. After such a tipping point is determined, clinical judgment will be applied as to the plausibility of the assumptions underlying this tipping point. This methodology is expected to inform what it would take to overturn study conclusions based on varying assumptions about missing data ([Ratitch, 2013](#); [Ratitch, 2014](#)).
- Per-randomized stratification analysis: The primary endpoint will be analyzed in the same manner as the primary analysis, except using per-randomized stratification factor from IXRS in the analysis.

